#### 9.10 Exclusion of Special Information During Hypothesis Validation and Reasons

Not applicable.

## **10. Data Management**

#### 10.1 Database Design

The CRF designer is responsible to annotate the final version of the blank CRF and describe in detail the necessary elements (e.g., variable name, length, type, range of the database variable, etc.).

The database designer determines the requirements for database establishment and database structure according to CRF and annotated CRF, and designs the database.

The database must be thoroughly tested to ensure that the contents and structure of the database are consistent with those of the CRF and annotated CRF, that the specified data are appropriately entered into the database, and that the entered data points are correctly exported into the corresponding database variables. The database can be officially released for use only after it is approved.

#### 10.2 Data Receipt and Data Entry

Data may be received by mail, courier with tracking for confidentiality, hand delivery by the monitor, web entry, or other electronic means. When the paper CRF data is received, it shall be recorded in the data receiving record form. After the completion of data receiving, the CRF shall be scanned and backed up; the data received via network or other electronic means shall be stored in the corresponding documents and records to confirm the data source.

Data entry can be double-entered by blind verification (two persons independently enter the data, and the inconsistency is resolved at the second entry), and double-entered by interactive verification (the second entry resolves the inconsistency between the two entries, and pays attention to the value of the first entry), manual review of single entry and other forms.

Prior to data entry, the data manager shall train the entry clerk or investigators on system operation or matters specific to this study.

After the completion of data entry, the database data shall be checked with original data to ensure that the database data are consistent with original data.

#### 10.3 Management of Data Verification and Query

Data verification includes manual inspection of data, and computer verification designed for identification error, invalid data range, data integrity, protocol violation and consistency inspection. Data administrator shall complete relevant procedures of preparing and approving the Data Verification Plan before the first data receipt to determine the data verification content. Programmer will program and test the verification procedure according to the finalized Data Verification Plan.

Based on the results of manual inspection and computer verification, the data administrator will resolve the doubtful data in the form of data query form, data processing agreement and self-evident correction, and update the database according to the answers or descriptions in relevant documents.

### 10.4 Database Lock and Data Archiving

The clinical trial database must be closed and locked to ensure the consistency and integrity of the data results, data analysis and data submitted to the official authorities.

When all data have been received and all data cleaning has been completed, all queries have been answered, all unanswered questions have been explained, the data review report has been confirmed, the division of statistical analysis dataset has been clarified, and the data quality control has been completed (the database quality is up to standard), the data administrator shall apply for database locking to the project team members. After being jointly confirmed by the investigators, the sponsor and project team members, the data editing authority of the database will be taken back to lock the database. After the database is locked, the data administrator shall transfer the data to the statistical analysis department in a timely manner. If data correction is required, the review and approval of Database Unlock Application Form shall be completed, and the database shall be unlock, so that corresponding personnel can enter the database to correct the data.

The data administrator shall establish the Data Management Project Folder, and shall be responsible for archiving the data or record files when they meet the conditions for archiving. Upon completion of the study, the data administrator will revoke the database access of relevant personnel, create a copy of the database, and archive the study documents and data management documents.

## 11. Feasibility Analysis

## 11.1 Probability Analysis of Success

- (1) According to the relevant clinical trials, it shows that such product is safe and reliable; and such product has been used in clinical practice for many years, and its safety and reliability have been verified.
- (2) The company producing the study medical device has rich experience. The product quality is reliable and meets the requirements of clinical trials; the device has passed the product registration inspection designated by NMPA (original CFDA).
- (3) The clinical institutions undertaking this trial have complete instruments, equipment and technical

resources.

(4) The investigators are excellent academic leaders in related disciplines in China, all of whom are physicians at or above the deputy director level, have rich clinical trial experience, have received GCP and relevant training, and can carry out treatment in strict accordance with the clinical trial protocol.

#### 11.2 Probability Analysis of Failure

- (1) Too many subjects withdrawing from the trial due to SAE;
- (2) Too many subjects lost to follow-up;
- (3) The IFU and label information of test product can not effectively instruct the operator;
- (4) Unskilled operation of investigators.

### **11.3** Conclusion

In conclusion, this product can be used for stapling lung tissues for the benefit of lung patients. This study has great feasibility and high possibility of success.

## 12. Quality Control of Clinical Trial

### 12.1 Quality Assurance

### 12.1.1 Definition

Quality assurance is defined as planned and systematic activities. These activities are established to ensure that the study, generation, citation (recording) and reporting of data are conducted in compliance with *Good Clinical Practice* (GCP) and applicable regulatory requirements.

#### 12.1.2 Audit

Audit refers to a systematic independent inspection of clinical trial-related activities and documents organized by the sponsor to determine whether the implementation of such activities and the recording, analysis and reporting of data comply with the clinical trial protocol, standard operating procedures, GCP and relevant applicable management requirements.

#### 12.1.3 Inspection

Inspection refers to the activities of the food and drug regulatory authority in reviewing and supervising relevant documents, facilities, records and other aspects of a clinical trial.

#### **12.1.4** Clinical trial monitoring

The sponsor shall be responsible for comprehensively tracking and monitoring the implementation of clinical

trial, ensuring that the trial is conducted in compliance with GCP and relevant regulations, and is in compliance with the trial protocol. NMPA (original CFDA) may also inspect the clinical trial during or after the trial is completed, and promptly notify the sponsor if investigators receive such notification.

The monitor will make periodic visits to the conduct and completion of the trial. Monitors will check the completeness of case records, the accuracy of case report form content, verify trial data, check the investigator's compliance with the trial protocol and the GCP, and ensure the accuracy of distribution, storage and counting of the study device.

### **12.2 Quality Control**

### 12.2.1 Definition

Quality control is defined as operational techniques and activities performed under a quality assurance system, such as monitoring, which is intended for verifying that the study-related activities meets the requirements.

Quality control should be applied to each stage of data processing to ensure that all data are credible and correctly processed.

### **12.2.2** Study monitoring

The authorized and qualified monitor will visit the clinical trial centers regularly according to the monitoring plan to verify the source data, the investigator's compliance with the protocol and regulations, and to assist the investigators.

## 12.2.3 Laboratory quality control

Each clinical trial center laboratory should establish unified standards for experimental test indicators, standard operating procedures and quality control procedures. Each experimental test item must adopt the national legal unit of measurement, and the test report items must be complete (including date, test item, test result and normal range), and relevant personnel should sign the report. Special inspection items must be specially assigned to be tested.

## 12.2.4 Quality control for other inspections

Each clinical trial center should establish unified evaluation criteria, standard operating procedures and quality control procedures for the evaluation of vital signs and damage. Each clinical trial center should evaluate the subject's condition according to the unified standard and standard operating procedures.

#### 12.2.5 Qualification of study personnel

The investigators participating in the clinical trial must have the professional expertise, qualification and ability of clinical trials, and pass the qualification review. The personnel requirements shall be relatively fixed.

### 12.2.6 Study staff training before study initiation

The sponsor is responsible for the training of study personnel before the start of the trial to help the clinical study personnel get a full understanding and understanding of the overall situation of the trial, protocol, CRF, etc.

## 13. Ethical Issues and Informed Consent of Clinical Trial

### **13.1 Ethical Considerations**

This clinical trial must be carried out in accordance with the *Declaration of Helsinki*, relevant medical device clinical trial regulations and laws in China. The study protocol must be approved by the Ethics Committee (EC) of the clinical trial institute before the study is initiated.

Before each subject is enrolled in the study, the study physician is responsible for explaining the contents of the trial to the subject in a verbal or written language understandable to the subject and carefully answering the subject's questions. Each subject must be given a written subject informed consent prior to enrollment. It is the responsibility of the study physician to obtain informed consent prior to each subject entering the study and to retain it in the study file.

This study is conducted based on the *Declaration of Helsinki*, *Good Manufacturing Practice* (GMP) for medical devices, *Good Clinical Practice* for medical devices, applicable laws and regulations in the People's Republic of China.

Based on ethical considerations, in accordance with GCP, relevant laws and regulations applicable within the territory of the People's Republic of China, the design and implementation of this study put the safety of subjects first on the requirements that the study medical device must be tested firstly when used under clinical conditions. Therefore, in this pre-clinical study, the biological safety of the materials used is tested firstly, and the purpose is to minimize the potential risks in the use of the materials. In order to fundamentally elucidate safety issues, various criteria for this study are also identified.

## 13.2 Approval of Study Protocol

Before the clinical trial, the investigators should submit the study protocol, informed consent form and other relevant documents to the medical ethics committee of the hospital where the study site is responsible for. The clinical trial can only be initiated after obtaining the approval of the Ethics Committee. Any amendment

to the study protocol must be approved by the Ethics Committee before implementation. Serious adverse events during the clinical trial should be reported to the Ethics Committee in written form in a timely manner.

## 13.3 Informed Consent Process and Informed Consent Form Text

Before each subject is enrolled in this study, the investigators are responsible for introducing the contents and description of the informed consent form to him/her or his/her guardian completely and comprehensively in written form.

The informed consent form should be written in a language understandable to the subject or his/her guardian. The informed consent form shall contain no content that may cause the subject to give up his/her legal rights and interests, and that exempt the clinical trial institution, the investigators, the sponsor or his/her agent from taking the responsibilities.

Each subject must be given a written subject informed consent prior to enrollment. It is the responsibility of the investigators to obtain informed consent before each subject enters the study and to retain it in the study file.

For an incapacitated subject, if the Ethics Committee agrees in principle and the investigators believe that the subject's participation in the clinical trial is in his/her own interests, he/she can also enter the clinical trial, but his/her guardian should sign and date it before the trial.

When the subject or his/her guardian is unable to read, a witness shall be present during the process of informed consent. After the informed consent form is explained in detail, the witness reads the informed consent form, which shall be consistent with the oral informed consent. After the subject or his/her guardian gives oral consent, the witness signs and dates the informed consent form, and the signature of the witness shall be on the same day as that of the investigator.

See the Informed Consent Form for details.

## 13.4 Personal Data and Data Protection

- All data obtained in clinical trials are subject to data protection. The investigators should not disclose the subject's name and other personal data (excluding date of birth/age and gender).
- (2) The CRFs and other documents transmitted to the sponsor will not contain names, but only the study code of the subject.
- (3) Similarly, the data used for statistical evaluation can only be performed under the study code of the subject. Only the investigator can identify the subject's name and other personal information through the study code.
- (4) During the study, if the subject name needs to be identified for medical reasons, all relevant personnel are obligated to keep it confidential.

## 14. Provisions for Reporting Adverse Events and Device Defects

#### 14.1 Adverse Event

Lobectomy (segmentectomy)

#### 14.1.1 Definition of adverse events

Adverse event (AE): refers to any adverse medical event occurring in the clinical trial process, no matter whether it is related to the investigational medical device or not.

#### 14.1.2 Adverse event grading

- (1) Mild: Symptoms inquired.
- (2) Medium: Symptoms that are actively described but can be tolerated.
- (3) Severe: Intolerable symptoms with objective manifestations.

#### 14.1.3 Reporting and handling of adverse events

All the adverse events and serious adverse events observed in the clinical trial should be clearly filled in the adverse event column of case report form. The duration of adverse event (i.e., the date of occurrence and disappearance of adverse event), severity, relationship with the clinical trial, and corresponding treatment and other handling measures should be recorded. Subjects occurring such event shall be followed up to end of the trial or the adverse event outcome.

#### 14.1.4 Correlation between adverse event and product

The correlation between all adverse events and study interventions must be judged by the investigators. The investigators then assessed based on temporal relationship and clinical experience. The followings are the evaluation criteria and judgment results of correlation:

- 1) The adverse event occurs within a reasonable time after the application of the device;
- (2) The adverse event can not be explained by other reasons;
- ③ The adverse event id relieved or disappeared after the the device is not applied;
- (4) The adverse event reappears after reapplication of the device.

Standa	urd (1)	2	3	4
Results				
Definitely related	+	+	+	+
Probably related	+	+	+	?
Possibly related	+	-	?	?

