# 8.1.5 Investigational medical device and control medical device or control diagnosis and treatment method

See the corresponding IFU for the diagnosis and treatment method with the investigational medical device and the reference medical device. The investigators shall truthfully record the usage for reference.

When subjects experience adverse events related to the stapler, the investigators should truthfully judge the correlation between adverse events and the test device.

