#### 8.1.7 Effectiveness evaluation method

# 8.1.7.1 Main effectiveness evaluation indicators, method and time for evaluation, recording and analysis

#### (1) Success rate of device cutting and anastomosis

**Justification for selection:** Through the mechanical transmission device, the stapler places two or multiple rows of staples prearranged in parallel and staggered rows in the component into the tissues that are aligned and need to be anastomosed. After passing through the tissues, the staples are blocked by the anvil jaw and

bend inward, forming a B-shaped staggered arrangement to anastomose the tissues together. Whether the stapler can successfully cut and staple the lung tissue is very critical to the video-assisted thoracoscopic surgery. If the cutting and stapling of lung tissue fails, the subject may need to be converted into thoracotomy, which will increase the risk of the subject. Therefore, in this clinical trial, the "success rate of device cutting and anastomosis" is selected as the primary endpoint, and the effectiveness of this product is evaluated by calculating the number of subjects required to be converted into thoracotomy due to the stapler.

**Evaluation time:** During the surgery.

Evaluation site: Tissues receiving linear stapler for pulmonary anastomosis.

**Evaluation method:** The transection and anastomosis of lung tissues are performed during the operation. The device is withdrawn after successful triggering. The cutting staple line is carefully checked for integrity, air leakage and bleeding. If all staple lines are complete, without air leakage or bleeding, it is judged that the cutting and anastomosis of the device is successful. If there is persistent air leakage and bleeding at the anastomosis site, and **conversion to thoracotomy is required**, it is judged as device cutting and anastomosis failure.

**Formula:** Device cutting and anastomosis success rate = number of subjects with successful anastomosis in each group/total number of subjects in this group  $\times 100\%$ 

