#### Table 3. Correlation evaluation table

Unlikely related	-	-	?	?		
Unrelated	-	-	-	-		
"+" indicates conformity, "-" indicates non-conformity, "?" Indicates unable to judge						

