- (10) When the investigators find unexpected adverse events of the study medical device during the clinical trial, they should modify the relevant contents of the informed consent form with the sponsor. After reporting to the Ethics Committee for review and approval according to the relevant working procedures, the affected subjects or their guardians should re-sign and confirm the revised informed consent form.
- (11) The investigators shall be responsible for making medical decisions related to the clinical trial. In case of any adverse event related to the clinical trial, the clinical trial institution and the investigators shall ensure to provide adequate and timely treatment, as well as processing for the subjects.
- (12)In case of any serious adverse event in the clinical trial, the investigators should immediately take appropriate therapeutic measures for the subjects, report to the management department of medical device clinical trial of the clinical trial institution in written form, and notify the sponsor in written form.
- (13) The investigators should record all adverse events occur and device defects found during the clinical trial, work with the sponsor to analyze the causes of the events, form a written analysis report, propose the comments on continuing, suspending or terminating the trial, and report to the Ethics Committee by the management department for clinical trial of medical device of the clinical trial institution for review.
- (14) The investigators should ensure that the clinical trial data are accurately, completely, clearly and timely recorded in the CRF.
- (15) The clinical trial institution and investigators shall ensure that the data, documents and records generated

from the clinical trial are authentic, accurate, clear and safe.

- (16)The clinical trial institution and investigators should accept the monitoring and verification by the sponsor, as well as the supervision by the Ethics Committee; and provide all required records related to the trial.
- (17) When the clinical trial institution and investigators need to suspend or terminate the clinical trial when they find that the risks outweigh the possible benefits, or the results are enough to judge the safety and effectiveness of the study medical device, they should inform the subjects and ensure that the subjects receive appropriate treatment and follow-up, report according to the provisions, and provide a detailed written explanation.

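### Does the missing row in the adverse-event causality table (14.1.4, Table 3) call for a change to the plan?

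*Combined protocol and SAP*

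**What the plan says.** Section 14.1.4 makes the rating compulsory: "The correlation between all adverse events and study interventions must be judged by the investigators". It bases the assessment on timing and clinical experience, then lists four criteria: (1) reasonable timing after use of the device; (2) no other explanation; (3) "The adverse event id relieved or disappeared after the the device is not applied"; (4) recurrence when the device is used again. Table 3 gives five rows, with `+` for met, `-` for not met and `?` explained as "Indicates unable to judge":

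| Category | 1 | 2 | 3 | 4 |
|---|---|---|---|---|
| Definitely related | + | + | + | + |
| Probably related | + | + | + | ? |
| Possibly related | + | - | ? | ? |
| Unlikely related | - | - | ? | ? |
| Unrelated | - | - | - | - |

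Under 14.1.3, "severity, relationship with the clinical trial, and corresponding treatment and other handling measures should be recorded", and subjects with an event are "followed up to end of the trial or the adverse event outcome". There is no default row and no rule for a pattern outside the table.

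**The concern.** Criteria 3 and 4 suit a product that can be stopped and restarted. A stapler is fired during the operation; section 8.1.7.1 says "The device is withdrawn after successful triggering", and the staples stay in the tissue. For postoperative staple-line bleeding or infection it may often be impossible to say whether the event eased because the device was no longer applied. That is an inference; the protocol does not discuss it.

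If criterion 3 is then scored `?`, a well-timed event with no competing explanation has no category, while the weaker case, with a competing explanation, is Possibly related. The order runs the wrong way for the events that point most clearly to the device. The five centres could fill the gap differently, and the raters know which stapler was used (8.1.3, item 4). At stake would be the consistency of the device-relatedness recorded for adverse events in a comparative safety evaluation.

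**Working it through.** The plan states no figure here, so the check is a count of patterns followed by a search for where the grade is used.

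**Inputs.** The five rows of Table 3. Each criterion can take three values, so there are 3^4 = 81 patterns.

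**Step 1: the gap.** Fix criteria 1 and 2 at `+` and let criterion 3 be `?` or `-` (2 values) and criterion 4 anything (3 values): 2 × 3 = 6 patterns, namely `++?+`, `++?-`, `++??`, `++-+`, `++--`, `++-?`. The only rows beginning `++` are Definitely and Probably, and both need `+` on criterion 3. So 0 of 6 have a row. This holds whether `?` in a row means strictly unable to judge or is read as any value.

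**Step 2: does any scoring of criterion 3 serve both cases?** Take timing `+` and criterion 4 `?`.

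| Criterion 3 | No other explanation | Other explanation, `?` strict | Other explanation, `?` as any value |
|---|---|---|---|
| + | Probably | no row | Possibly |
| ? | no row | Possibly | Possibly |
| - | no row | no row | Possibly |

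On the strict reading, 0 of 3 scorings place both events. On the any-value reading, 1 of 3 does: scoring relief as `+` for an event that resolves after the stapler is withdrawn gives Probably and Possibly, in the right order. The gap is then limited to `++` events that do not resolve or whose relief cannot be judged.

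**Step 3: overall coverage.** Strictly, 5 of 81 patterns have a row. With `?` as any value, Probably covers 3 patterns (including Definitely), Possibly 9, and Unlikely 9 (including Unrelated): 3 + 9 + 9 = 21 of 81. On either reading most patterns lie outside the table, so it works as a set of anchor cases beside clinical judgement.

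**Step 4: where the grade is used.**

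- Primary endpoint (8.1.7.1) and success criterion (9.5): intraoperative result and confidence interval; Table 3 is not used.
- Staple-line bleeding and infection (8.1.8, items 2 and 4): counted from clinical findings.
- SAE and AE incidence (8.1.8, items 5 and 6): subjects with any such event over all subjects in the group. The rule treating staple-line events as SAEs names no Table 3 category.
- Analysis (9.7.1): adverse events are listed; no comparison by relatedness is specified.
- SAE handling (14.2.2): applies to any SAE, whatever its grade.

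**Step 5: attribution recorded elsewhere.** Section 8.1.5: "the investigators should truthfully judge the correlation between adverse events and the test device". Section 22.2, item 13, has investigators "work with the sponsor to analyze the causes of the events". Section 8.1.7.1 asks whether a conversion was caused by the stapler. Section 8.1.7.2, item 3, asks whether drainage beyond 7 days is device-related. Footnote 10 to 8.2.5.5 asks for the reason and any link to the stapler for conversion, repair, dehiscence and other intraoperative complications.

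**The case for a change.** The strongest case for acting is that every event must be rated, and one natural pattern has no category. Clinical experience permits a judgement but does not say which category to enter. Section 16.1.3, item 6, names frequent failure to judge SAE causality as an example of a significant deviation, so the rating is not optional. The other attribution duties give no graded scale. They also cover intraoperative events better than postoperative bleeding or infection, where footnote 12 asks only why the event was confirmed. Unblinded raters at five centres with undefined discretion are undesirable, and an added row and scoring note would need no new examinations.

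Much of this stands as description. The missing row, the inverted order and the lack of a default are real. What does not stand is the step to a needed change. The duty in 16.1.3 is to make a judgement, which an investigator can do without a matching row. Postoperative staple-line bleeding and infection enter the safety comparison through their own incidence rates, whatever grade is written beside them. A note to mark relief as unjudgeable when it cannot be assessed would not settle whether resolution after withdrawal of the stapler counts as assessable, which is the ambiguity itself. Nor is timing neutral: this version is dated 25 March 2019 and the last subject was due to finish that month (8.1.6.5). If that timetable held, most events would already be rated, and a new row would chiefly prompt re-rating by people who know the allocation. Showing old and new ratings side by side would disclose that bias without removing it.

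**Conclusion.** No change to the plan. Table 3 is incomplete: 0 of 6 patterns with good timing, no other explanation and criterion 3 not met or not judgeable have a row, on either reading of `?`. The stronger claim, that no scoring of criterion 3 serves both kinds of event, depends on the strict reading. This is missing detail that investigators can fill by the clinical judgement 14.1.4 already allows. It reaches only the recorded relatedness category, so following the plan as written would not produce a wrong estimate, test or conclusion.

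The conclusion rests on two points: relatedness is recorded and at most listed, with no planned comparison by grade; and the March 2019 completion date was roughly kept. The documents give neither the number of events that would fall in the gap nor the direction of any misgrading, and the pattern counts are not likelihoods. If a comparison of device-related events between the groups were added, the gap would matter more.
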